#### 6.1.1 Sample size calculations for safety

The goal of the safety evaluation for this study is to identify safety concerns associated with product administration. This participant population is at risk for at least two different categories of AEs—vaccine-related reactogenicity (or other side effects) and the development of a flare of SLE disease activity. For this reason, we will treat these events separately for the following calculations.

##### 6.1.1.1 Vaccine-related AEs

The ability of the study to detect SAEs (see Section 11) can be expressed by the true event rate above which at least 1 SAE would likely be observed and the true event rate below which no events would likely be observed. Specifically, for the vaccine arm of the study ( $n = 16$ ), there is an 81.5% chance of observing at least 1 event if the true rate of such an event is 10% or more; and there is an 85.1% chance of observing no events if the true rate is 1% or less.

Probabilities of observing 0, 1 or more, and up to 5 or more events among arms of size 16 are presented in Table 6-1 for a range of possible true AE rates. These calculations provide a more complete picture of the sensitivity of this study design to identify potential safety problems with the vaccine.

**Table 6-1 Probability of observing 0 events, 1 or more events, and up to 5 or more events, among arms of size 16, for different true event rates**

True event rate (%)	Pr(0/16)	Pr(1+/16)	Pr(2+/16)	Pr(3+/16)	Pr(4+/16)	Pr(5+/16)
1	0.851	0.149	0.011	0.001	0	0
5	0.440	0.560	0.189	0.043	0.007	0.001
10	0.185	0.815	0.485	0.211	0.068	0.017

For this study, suspected adverse reactions are any AEs for which there is a reasonable possibility that the vaccine caused the event, suggesting a causal relationship. Using exponential hazard time-to-event methods in simulation (N = 1000), if there is a 5% chance per year of a related non-serious AE, we would be expected, on average, to have 0.8 incidents (95% CI: <1, 2.5) during the 12 months of follow-up in this study. If the AE rate is 7.5%, we would expect, on average, to have 1.1 events (95% CI: <1, 3.2); if the AE rate is 10%, we would expect, on average, to have 1.6 events (95% CI: <1, 3.9).

#### 6.1.1.2 Flare of SLE disease activity

This subject cohort may be expected to have an SLE flare rate as high as 20% (defined as an increase of 4 or more in SLEDAI (100) between study visits), indicating that a more conservative threshold is appropriate. For example, if we base the expected SLE flare rates on the control arm of Ruiz-Irastorza et al (101), where the monthly percentage of patients with flares was 3.9%, we expect a possibly higher rate of SLE flare than that described above. Using exponential hazard time-to-event methods in simulation (N = 1,000), if there is a 3.9% chance per patient-month of flare, we would be expected, on average, to have 6.1 incidents (95% CI 2.1, 10.1) per year of follow-up in this study. If flare events are independent, then there is 14.4% chance of a participant having 2 flare events in one year.

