## 6 Statistical considerations

### 6.1 Accrual and sample size calculations

Recruitment for this single arm study will target enrolling 16 low-risk, HIV-uninfected adult participants, aged 18-50, who have also been diagnosed with SLE.

The primary purpose of this study is to explore the possibility that AIDS VAX® B/E may induce bnAbs in a population of participants diagnosed with SLE and to closely monitor participant safety. Since enrollment is concurrent with receiving the first study vaccination, all participants will provide some safety data. However, for immunogenicity analyses, it is possible that data may be missing for various reasons, such as participants terminating from the study early, problems in shipping specimens, low cell viability of processed peripheral blood mononuclear cells (PBMCs). Immunogenicity data from 17 phase 1 and 2 phase 2a HVTN vaccine trials, which began enrolling after June 2005 (data as of September 2014), indicate that 15% is a reasonable estimate for the rate of missing data at day 182. For this reason, the sample size calculations in Section 6.1.2 account for 15% of enrolled participants having missing data for the primary immunogenicity endpoint.

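### The 14.4% chance of two flares in a year is a first-flare probability squared; the protocol's own rate gives about 8%, and the 6.1 beside it needs a label

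*Combined protocol and SAP*

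**What the plan says.** Section 6.1.1 treats SLE flare as a category of adverse event separate from vaccine reactions. Section 6.1.1.2 takes a monthly flare percentage of 3.9 from the control arm of a cited study and applies an exponential-hazard simulation with 1,000 runs. It concludes that "if there is a 3.9% chance per patient-month of flare", then "we would be expected, on average, to have 6.1 incidents (95% CI 2.1, 10.1) per year of follow-up in this study". The section closes with: "If flare events are independent, then there is 14.4% chance of a participant having 2 flare events in one year". It gives no formula for the 14.4%. It also does not say whether the 6.1 counts participants with a first flare or all flares, repeats included.

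The other inputs are 16 participants (Section 6.1) and 12 months of visits per participant (Section 3, duration per participant).

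**The concern.** The two closing sentences of 6.1.1.2 should follow from the same 3.9% rate. The first does, as a count of participants. The second appears to be the one-year probability of a first flare multiplied by itself. That would be the chance of a flare in each of two separate full years, or in each of two different participants. It is not the chance of two flares in one participant in one year, because a second flare can only occur in the time left after the first.

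The trial has a single arm and no concurrent unvaccinated group, so the expected flare frequency in this section is a natural yardstick for anyone reviewing flares as they occur. The 14.4% is the section's only statement on repeat flares. If it is too high, repeat flares that are seen will look more ordinary than the protocol's own rate says they are. The unlabelled 6.1 adds a second ambiguity, because the sentence after it is about repeat events.

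**Working it through.** **Inputs.** Monthly flare probability p = 0.039, constant hazard, independent flares and a one-year horizon (all Section 6.1.1.2); n = 16 (Section 6.1); 12 months of follow-up (Section 3).

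**Step 1: reproduce the stated figures.**
- One-year chance of at least one flare: q = 1 − (1 − 0.039)^12 = 1 − 0.961^12 = 0.3796.
- Expected participants with at least one flare: 16 × 0.3796 = 6.07, which matches 6.1.
- Spread: SD = √(16 × 0.3796 × 0.6204) = 1.94. The normal interval is 6.07 ± 1.96 × 1.94 = 2.3 to 9.9, and the binomial 2.5% and 97.5% quantiles are 2 and 10. Both are close to the stated 2.1 to 10.1.
- q² = 0.3796² = 0.1441, which matches 14.4%.

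So 6.1 and 14.4% come from the same q. Reading 0.039 directly as the hazard gives 1 − e^(−0.468) = 0.3737, whose square is 0.1397. That does not match.

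**Step 2: the chance of two or more flares in the same 12 months.**
- Monthly binomial: 1 − 0.961^12 − 12 × 0.039 × 0.961^11 = 0.0775.
- Poisson with mean m: 1 − e^(−m)(1 + m). With m = 12 × 0.039 = 0.468 this is 0.0807. With m = −12 × ln 0.961 = 0.4774, the hazard that matches q, it is 0.0834.
- Simulating two successive exponential waiting times that must both end within 12 months gave 0.084.

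| Model | Two or more | Exactly two | Expected of 16 with two or more | At least one of 16 with two or more | Two or more, given at least one |
|---|---|---|---|---|---|
| Binomial, 12 months | 7.7% | 6.7% | 1.24 | 72.5% | 20.4% |
| Poisson, mean 0.468 | 8.1% | 6.9% | 1.29 | 74.0% | 21.6% |
| Poisson, mean 0.4774 | 8.3% | 7.1% | 1.33 | 75.2% | 22.0% |
| Implied by 14.4% | 14.4% | – | 2.30 | 91.7% | 37.9% |

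The fourth column is 16 × P, the fifth is 1 − (1 − P)^16 and the last is P/P(at least one), where P is the chance of two or more.

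**Step 3: what rate would 14.4% need?** Solving 1 − e^(−m)(1 + m) = 0.144 gives m = 0.666 per year, or 0.0555 per month (0.0563 under the binomial). With the same rate in every participant, the expected number with at least one flare would then be 7.8 (8.0 under the binomial), not 6.1.

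**Step 4: the label on 6.1.** If every flare is counted, the expected total is 16 × 12 × 0.039 = 7.49, with Poisson quantiles 3 and 13. The 6.1 is therefore a count of participants, not of flares.

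**The case against.** The strongest objection is about weight. Nothing in the plan uses the 14.4%. The sample size rests on detecting broadly neutralizing antibodies (Section 6.1.2). The pause rule in Table 11-8 counts flares across the trial, and severe flares go to prompt review one by one. The planned SELENA-SLEDAI outputs in Section 6.3.3.4 do not analyse repeat flares. All of this stands, and it limits the consequence. It does not make the number right.

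A second objection is that 14.4% and 6.1 can coexist if flare rates differ between participants. With a gamma-mixed Poisson of shape 1 and a 0.3796 chance of at least one flare, the chance of two or more is exactly 0.3796² = 14.4%. That is a fair qualification to Step 3, whose back-calculation assumes a common rate. The protocol states no such mixture, however; it uses a single exponential hazard with independent events. If the mean is held at 0.477 per year, gamma shapes from 4 to 1 give about 9% to 10%, still well below 14.4%.

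A third is that Section 6.1.1.1 does little to settle what an incident is. There, "if the AE rate is 10%, we would expect, on average, to have 1.6 events", and 16 × 0.10 = 1.6, as 16 × 0.05 = 0.8 at 5%. But at such low rates a total with repeats is nearly the same: 16 × −ln 0.90 = 1.69 and 16 × −ln 0.95 = 0.82. The 7.5% case is stated as 1.1, against 16 × 0.075 = 1.2. Those figures fit the participant reading but are weak evidence for it. The reading of 6.1 rests on Step 1, which is enough.

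Finally, a 20-month horizon (the total study duration) would give 14.3% for exactly two flares. The sentence says one year and each participant is followed for 12 months, so this does not rescue it.

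**Conclusion.** The concern holds. The 14.4% is a squared first-flare probability and does not answer the question the sentence poses. On the protocol's own assumptions (3.9% per patient-month, the same constant rate in all participants, independent flares, 12 months without dropout), the chance of two or more flares is 7.7% to 8.3%, and of exactly two about 7%. The stated value is too high by a factor of about 1.7 to 1.9 (14.4/8.3 to 14.4/7.7) for two or more.

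The 6.1 and its interval are sound, to within rounding and simulation error, as the expected number of participants with at least one flare; only the wording is unclear. The effect is confined to the safety expectations stated in 6.1.1.2. It is worth correcting because this is a calculated safety probability in the statistical section of a trial with no concurrent control group.

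**What to change.** In Section 6.1.1.2:

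1. Replace the last sentence with: *With independent flares at a constant 3.9% per patient-month, the same in every participant, the chance of two or more flares in 12 months is about 8% (about 1.3 of 16 participants).*
2. Change the 6.1 incidents to: *6.1 participants with at least one flare (about 2 to 10).*
3. Only if a total flare count is wanted, add: *about 7.5 flares in total (about 3 to 13), assuming a constant rate, independent recurrent flares and 16 participants followed for 12 months without dropout.*

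The cost is two edited sentences. Sample size, visits, data collection, analyses and the pause rule stay as they are.

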#### 6.1.2 Sample size calculations for immunogenicity

The primary immunogenicity endpoint will be the production of bnAbs. This will be defined as a nAb geometric mean titer (GMT) greater than 100 against a standard HIV-1 pseudovirus panel. The sample size of 16 was selected such that if the true proportion of participants producing bnAbs in this population is at least 10 percent, we will have 81.5% probability of detecting bnAbs in at least one participant. If there is a dropout rate of 10% then we will still have a 77.1% probability of detecting bnAbs in at least one participant ([Table 6-2](#)).

**Table 6-2 Probability of detecting bnAbs in at least one participant, among different arm sizes, for different true event rates**

Number of Participants	True Population Percentage of SLE Participants Producing BnAbs			
	1%	5%	10%	25%
12	0.114	0.460	0.718	0.968
14	0.131	0.512	0.771	0.982
16	0.149	0.560	0.815	0.990
18	0.165	0.603	0.850	0.994

## 6.2 Randomization

Since there is only one treatment assignment in this study, participants will not be randomized.

## 6.3 Statistical analyses

Analyses for primary endpoints will be performed using SAS and R. All other descriptive and inferential statistical analyses will be performed using SAS, StatXact, or R statistical software.

No formal multiple comparison adjustments will be employed for multiple safety endpoints or multiple primary immunogenicity endpoints. However, multiplicity adjustments will be made for certain immunogenicity assays, as discussed below, when the assay endpoint is viewed as a collection of hypotheses (eg, testing multiple peptide pools to determine a positive response).

### 6.3.1 Analysis variables

The analysis variables consist of baseline participant characteristics, safety, and immunogenicity for primary- and secondary-objective analyses.

### 6.3.2 Baseline comparability

Selection of historical controls from RV328 that were vaccinated and underwent immunogenicity testing on a similar timeline will serve as a suitable non-SLE control group. Although, given the small study population (40 total), all 30 who received AIDS VAX® B/E will be included as comparators.

The 125 SLE patients in the CHAVI 005 study, with similar demographic characteristics to this study population, will serve as a cross-sectional, unvaccinated SLE control group for immunogenicity comparisons.

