As part of the original Center for HIV-AIDS Vaccine Immunology (CHAVI) program, the CHAVI 005 study examined a group of participants with known autoimmune disease to determine if any had undiagnosed HIV-1 infection, and if their plasma had any evidence of existing neutralizing antibodies that could account for the previously noted disparity between SLE and HIV-1 infection. This cohort, including 100 participants without autoimmune disease and 125 participants with SLE, was recruited from the Duke Lupus Clinic between 2005-2011. The CHAVI program tested this cohort using both HIV-1 antibody and viral load assays and found that none of the participants were HIV-1-infected. Testing of a subset of the participants did not reveal evidence of HIV-1 neutralizing antibodies or reactivity with HIV-1 Env proteins, although it should be noted that the study participants did not receive any HIV-1 vaccinations. Samples from this study are available for testing using the same assays planned for the present study, and for all participants, there are plasma, serum, and PBMC stored in the CHAVI Repository. This cohort was drawn from the same patient population at Duke that will be recruited for this study, and because the second of two sites participating in this study is in Alabama, the demographics of the two populations is likely to be similar. We can therefore use the SLE patients in the CHAVI 005 study as unvaccinated SLE controls, serving as a cross-sectional comparison group.

The primary outcome is to evaluate whether persons with SLE vaccinated with an HIV-1 vaccine will develop HIV-1 nAbs with greater breadth and potency than persons without SLE. In addition, our immunogenicity hypotheses are that this cohort of participants with SLE will make a qualitatively and quantitatively superior antibody response against HIV-1. An additional secondary outcome will address the hypothesis that the vaccine regimen will be safe and well tolerated by participants. The proposed number of participants is not sufficiently powered to detect uncommon or rare events. Participants will be monitored for sentinel events indicative of SLE disease activation (ie, SLE flare); detection of an SLE flare will trigger additional review.

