### 7.1 Inclusion criteria

#### General and Demographic Criteria

1. **Age** of 18 to 50 years
2. **Weight** > 110 pounds
3. Meets **ACR criteria for the classification of SLE** (86, 87, 105) with serologic evidence of disease including a positive test for antinuclear antibodies at a titer of 1:640 or greater, or the presence of a positive test for antibodies to dsDNA, or the presence of anti-Sm, anti-RNP, or anti-Ro antibodies, as documented by medical records and as assessed by a rheumatologist or designee.
4. Currently taking hydroxychloroquine for SLE and for at least 6 months prior to enrollment
5. **Access to a participating HVTN CRS** and willingness to be followed for the planned duration of the study
6. Ability and willingness to provide **informed consent**

7. **Allows ongoing access to medical records pertaining to their rheumatologic disease**
8. **Assessment of understanding:** volunteer demonstrates understanding of this study; completes a questionnaire prior to first vaccination with verbal demonstration of understanding of all questionnaire items answered incorrectly
9. **Agrees not to enroll in another study** of an investigational research agent before the last required protocol clinic visit

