### **SLE status. The following criteria must be verified by a rheumatologist or designee**

6. **Currently with active lupus** as defined by a Systemic Lupus Erythematosus Disease Activity Index (100) (SELENA-SLEDAI) > 4 (106) (see [Appendix G](#)).
7. **Documented SLEDAI score of > 20 in medical record at any time** indicating severe activity (106), or evidence of moderate disease activity (SELENA-SLEDAI > 6) within the last six months, (see [Appendix G](#)).
8. **Has had a condition listed on the Systemic Lupus International Collaborating Clinics/American College of Rheumatology Damage Index (SLICC/ACR DI) (105)** or has had an increase in the SLICC/ACR DI score within the last 12 months other than cataracts, premature ovarian failure or diabetes mellitus with approval of the PSRT  
<http://www.clinexprheumatol.org/article.asp?a=2697>
9. A history of **central nervous system (CNS) disease**

10. **Thrombotic event within the past 12 months in association with confirmed antiphospholipid antibody**
11. **A history of renal disease** (SLE-related renal injury) confirmed by prior biopsy, active urine sediment, or proteinuria
12. **Prednisone dose** > 10 mg/day for more than 6 months within the past year
13. **Administration of anti-B-cell therapy** (rituximab or belimumab) or any investigational research agents used to treat SLE within the preceding 2 years
14. **Administration of cyclophosphamide** within the preceding year; or administration of mycophenolate mofetil within the last 6 months; or administration of methotrexate, leflunomide, or azathioprine within the last 3 months
15. **Administration of any investigational immunosuppressant medication** within the last year
16. **Administration of other immunosuppressive medications** not listed above, with the exception of topical steroids, topical immunosuppressives (eg, cyclosporine, FK506), or ophthalmic immunosuppressives (eg, steroids, cyclosporine), within 6 months before first vaccination, unless approved by the HVTN 121 PSRT

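### All 125 CHAVI 005 lupus patients are the unvaccinated SLE control, with no activity or treatment criterion; comparisons of markers that are not HIV-specific could be biased

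*Combined protocol and SAP*

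**What the plan says.** Section 6.3.2 (Baseline comparability) takes "The 125 SLE patients in the CHAVI 005 study, with similar demographic characteristics to this study population" and states that they "will serve as a cross-sectional, unvaccinated SLE control group for immunogenicity comparisons". It plans no selection among the 125.

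Section 4.3 gives the background: "This cohort, including 100 participants without autoimmune disease and 125 participants with SLE, was recruited from the Duke Lupus Clinic between 2005-2011". It also says "This cohort was drawn from the same patient population at Duke that will be recruited for this study", expects similar demographics at the second site, and concludes: "We can therefore use the SLE patients in the CHAVI 005 study as unvaccinated SLE controls, serving as a cross-sectional comparison group". Stored plasma, serum and PBMC are available for the assays planned in HVTN 121. No disease-activity, hydroxychloroquine or immunosuppressant criterion is given for CHAVI 005.

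Sections 7.1 and 7.2 define the HVTN 121 population:

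- Inclusion 1 limits age to 18-50, and inclusion 4 requires "Currently taking hydroxychloroquine for SLE and for at least 6 months prior to enrollment".
- Exclusion 6 removes anyone "Currently with active lupus", set at SELENA-SLEDAI above 4. Exclusion 7 removes scores above 6 in the last six months or above 20 at any time.
- Exclusions 9 and 11 remove CNS and renal disease.
- Exclusions 12-16 set limits on prednisone, anti-B-cell agents, cyclophosphamide, mycophenolate, methotrexate, leflunomide, azathioprine and other immunosuppressants.

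Section 6.3.4.2 allows regression adjustment of the AUC-MB comparison between cohorts. Its examples are age, gender and other immune responses. Section 6.3.4.1 makes comparisons of quantitative assays with controls from other studies optional.

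**The concern.** The HVTN 121 participants are a lupus population filtered on activity and treatment. As described, the CHAVI 005 patients are an unfiltered clinic cohort from some years before. A shared clinic and similar demographics do not make the two groups alike on the variables used as the filter.

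Those variables plausibly affect cytokines, B- and T-cell phenotype and repertoire. The protocol itself treats them as relevant: Section 4.1.1 names chloroquine as an example of a drug that modulates immune tolerance, and Section 4.1.2 stresses low baseline activity and discusses immunosuppressants alongside vaccine response.

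At stake is how a cross-sectional difference is read. If the 125 include patients with more active disease or heavier immunosuppression, a difference from HVTN 121 could be produced, or a real one hidden, by patient mix and then credited to the vaccine or to its absence of effect.

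**Working it through.** **1. Which comparisons are exposed.** Section 6.3.4 places immune activation under immunogenicity analysis, and Section 6.3.2 assigns CHAVI 005 to immunogenicity comparisons. Section 10.3 lists CHAVI 005 with RV328 as a control for the neutralizing assay and for applicable secondary and exploratory endpoints. A CHAVI 005 comparison of non-HIV-specific markers is therefore within the stated scope, although no specific contrast or test is laid out.

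- HIV-specific neutralizing and binding antibody: Section 4.3 reports "Testing of a subset of the participants did not reveal evidence of HIV-1 neutralizing antibodies or reactivity with HIV-1 Env proteins". Unvaccinated controls should be near the floor whatever their activity or drugs, so little bias is expected.
- Cytokines, B/T-cell phenotype and B-cell repertoire: unvaccinated patients have no such floor, so a difference in patient mix can carry through.

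**2. The plan's own figures.** The plan gives no power, SD or error rate for the CHAVI 005 comparison. The 81.5% in Section 6.1.2 reproduces as 1 − 0.9^16 = 0.815, but it does not involve controls.

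**3. Illustration of bias.** All shifts are assumed, because the documents give no CHAVI 005 activity or treatment data.

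- Inputs: 16 vaccinees and 125 controls (Sections 6.1 and 6.3.2); a marker in SD units; nominal two-sided 5% (assumed); no vaccine effect.
- SE = √(1/16 + 1/125) = √0.0705 = 0.2655 SD.
- Shift b = (fraction of the 125 who would be ineligible) × (their difference in SD).
- P(reject) = Φ(b/SE − 1.96) + Φ(−b/SE − 1.96).

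| Assumed mix | b (SD) | b/SE | P(reject) |
|---|---|---|---|
| none | 0 | 0 | 5.0% |
| 30% ineligible, 0.5 SD apart | 0.15 | 0.565 | 8.7% |
| 50% ineligible, 0.5 SD apart | 0.25 | 0.942 | 15.6% |

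Section 6.1 expects 15% missing data (16 × 0.85 = 13.6). With 14 evaluable vaccinees, SE = √(1/14 + 1/125) = 0.282, and a 0.25 SD shift gives 14.4%, so the picture is unchanged.

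**4. Precision cost of restricting the controls (16 vaccinees).**

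| Controls kept | SE (SD) | Change from 125 |
|---|---|---|
| 125 | 0.2655 | – |
| 87 (30% removed) | √(1/16 + 1/87) = 0.272 | +2% |
| 62 (50% removed) | √(1/16 + 1/62) = 0.280 | +6% |
| 40 (68% removed) | √(1/16 + 1/40) = 0.2958 | +11% |

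With 14 vaccinees, the difference detectable with 80% power goes from 0.79 SD (125 controls) to 0.85 SD (50 controls) or 0.94 SD (25 controls). The cost is small because the vaccinees dominate the SE.

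**The case against.** The strongest reply is that the plan does not rest its main conclusions on this comparison. RV328 supplies the vaccinated non-SLE comparator (Section 4.3) and is the comparator named for immune activation (Section 4.1.2). Section 6.3.4.3 specifies only plots, summaries and changes from baseline, with no CHAVI 005 test. Day 0 samples for phenotyping, cytokines, binding and neutralizing antibody (Appendix E) give each participant a pre-vaccination reference that meets every entry criterion. The list of adjustment covariates in Section 6.3.4.2 is open-ended. Section 4.1.2 already concedes that, after multiplicity correction, significant differences from historical controls cannot be expected.

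Most of this stands, and it limits the point to comparisons that are not HIV-specific. It does not remove it. Sections 6.3.2 and 10.3 leave those comparisons open, the adjustment is optional and names neither activity nor treatment, and change from day 0 does not repair a cross-sectional contrast if one is reported. Using the same laboratories (Section 10.3) deals with assay differences, not with patient mix.

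Three stronger readings are tempting but unsupported:

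- That activity and treatment do confound the comparison. CHAVI 005 is not described on either, so this is not known.
- That HVTN 121 participants are free of immunosuppression. Exclusion 12 bars only prednisone above 10 mg/day for more than 6 months in the past year, exclusion 14 admits past users after washout, and exclusion 16 lets the PSRT approve other agents.
- That the same people appear in both groups. The shared clinic makes this possible and no criterion prevents it, but nothing shows that it happened.

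**Conclusion.** The point holds in a limited form. Section 6.3.2 applies one unselected control group to all immunogenicity comparisons, on grounds that do not address the main ways in which HVTN 121 selects its patients. For HIV-specific antibody the consequence is slight, and a reader should not infer that the primary neutralization result is undermined. For cytokines, cell phenotype or repertoire, any CHAVI 005 comparison could be biased in either direction.

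An imbalance of 0.15 to 0.25 SD would raise a nominal 5% error rate to about 9-16%. Those shifts, the test and its level are assumptions. The documents establish the gap in the comparability argument, not the size of the imbalance. The change is worth making because it is cheap and its precision cost is small.

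**What to change.** Amend Section 6.3.2 as follows.

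- For endpoints that are not HIV-specific, limit the CHAVI 005 controls to patients who at sampling met the HVTN 121 criteria on age, hydroxychloroquine, disease activity, renal and CNS disease, and immunosuppressants (inclusions 1 and 4; exclusions 6, 7, 9, 11 and 12-16), as far as records show.
- Exclude from the controls anyone also enrolled in HVTN 121.
- Show all 125 as a sensitivity analysis.
- State, here and in Section 6.3.4.3, that within-participant change from day 0 is the main analysis of immune activation.
- If activity and drug records are unavailable, use CHAVI 005 only as a negative control for HIV-specific antibody.

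The cost is SAP wording and a records filter, with no change to enrolment, vaccination or visits. The controls become fewer, with an SE about 11% wider if 40 remain, although fewer stored samples need assay. Whether CHAVI 005 holds the records is an assumption, and criteria that look back months or years may be only partly checkable.
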